15.5 Development of the Performance Goal (PG) – Primary Efficacy Endpoint

15.5.1 Rationale

The FDA has indicated that venous stent trials should establish a performance goal to be met in the study, as described in Rocha-Singh et al.⁸ In that article, the authors performed a literature search and identified 11 controlled studies of femoropopliteal stenting in *arterial* stenotic lesions where the patency rate of the control arm was described. The studies were all prospective, with clearly defined enrollment criteria and with pre-specified patency definitions (all using quantitative rather than qualitative criteria). Independent investigators performed the review of the anatomic endpoints in four of the five included studies (core laboratories).

The historical literature for venous stenting is considerably different. A total of 6 studies (See Table 15.5.2.a and Table 15.5.2.b) have been included in our review, all of which are retrospective, single arm, uncontrolled, and with variable populations. The endpoint of "primary patency" is qualitative in some studies, i.e., based on absence of symptoms in most cases, and quantitative in others, using an assessment of in-stent stenosis by an imaging modality such as venography or Doppler ultrasound (DUS). None of the studies used an outside, objective independent core laboratory assessment of predefined patency. Without independent core laboratory assessment of patency, there is an inherent, if subconscious bias to report higher patency rates, as authors are biased to report the best results possible.

Despite these issues, a clinical evaluation based on a performance goal is the best available approach in the absence of an already marketed comparator. These issues support a delta of 10% from the literature-based patency rate in the determination of the performance goal. This conclusion is supported by the variability in primary patency rates reported, ranging from 61%-80% (19% delta) for PT and 83-98% (15% delta) for NT patients (See Table 15.5.2a and Table 15.5.2b).

15.5.2 Historical Patency Rates

A literature search was performed to identify peer-reviewed articles with original data about patency rates at 12 months in patients with chronic venous obstruction who underwent iliofemoral stenting. Two separate searches were conducted: the first one had been done previously (10/9/2011) for company review; the second one was repeated July 31, 2013. Both searches used the terms listed below with limits of English, after 2000, and

- "human",
- "venous stenting"

STE-HUM-007P US Clinical Protocol Revision C

Confidential

Page 40 of 70

- (("May-Thurner syndrome" OR "May Thurner syndrome") AND stent)
- "Iliac vein" AND stent
- (("venous occlusion" OR "venous insufficiency" OR "postthrombotic syndrome" OR "venous thrombosis" OR "venous obstruction" OR "iliac vein compression syndrome" OR "iliofemoral vein" OR "iliocaval vein" OR "femoral vein") AND stent).

A total of 36 articles (31 in the original search, and 5 in the update search) were identified for further review, and 6 were included in development of the Performance Goal. Only papers that reported primary patency data at 12 months for adult patients who underwent stenting for chronic venous obstruction without adjuvant procedures were included.

The exclusion criteria for the articles we used for the historical control were based on our intended study population. Studies were excluded from the control if the study included:

- Patients who had thrombolysis, thrombectomy, or creation of an AV fistula during the index procedure, or other adjuvant procedures (endovenous laser ablation)
- Patients who did not have stenting of the iliofemoral tract
- Adolescents or pediatric patients
- Patients with acute venous thrombosis

A weighted average of qualitative patency, i.e., patients free from reintervention *and* free from occlusion (flow present on DUS) *and* free from ≥50% stenosis (per venogram or DUS lumen diameter) was created.

Author, date	Limbs	≥50%	Limbs	Quantitative	Limbs with	
	studied at		occluded	patency rate	quantitative	
	1 yr	N (%)			patency	
Meng, 2011 ⁶	143	1	2	(97.9%)	140	
Neglén, 2007 ⁵	132	(1%)	(6%)	(93%)	123	
Total	275			(95.5%)	262.8	

Table 15.5.2.a. NT Patients (no prior history of thromboembolic event)

Author, date	Limbs	≥50%	Limbs	Qualitative	Limbs with	
	studied	stenosis	stenosis occluded		qualitative	
	at 1 yr	N (%)			patency	
Rosales, 2009 ⁹	34 ^a	Not eval		(75%)	25.5	
Neglén, 2007⁵	135	(3%)	(17%)	(80%)	108	
Kölbel, 2009 ¹⁰	40			(78) ^b	31.2	
Wahlgren, 2010 ¹¹	11	(1 pt, in PP)		(61%) ^b	6.7	
Kurklinsky, 2011 ¹²	91	Not eval	(17%)	(81%)	73.7	
Total	311			(78.8%)	245.1	

Table 15.5.2 b. PT Patients (history of prior thromboembolic event)

a Patients were only studied if symptomatic.

b Authors made note of patients in the re-intervention group who had stenosis, so we concluded some evaluation of in-stent stenosis was included in assessment of primary patency. Possibly, it could represent only those patients with in-stent stenosis with symptoms.

In addition to these data, we used evidence from Neglén³ and Neglén and Raju¹³ that there are patients with greater than 50% restenosis who are asymptomatic, and therefore unlikely to be evaluated for flow under usual clinical practice. These studies estimated that approximately 3% of asymptomatic patients had re-stenoses of 50% or greater. Table 15.5.2.c shows this adjustment to the rates in Table 15.5.2.b. (This phenomenon was noted only in PT patients, hence no adjustments were made to Table 15.5.2.a.)

Author, date	Limbs	≥50%	Limbs	Quantitative	Limbs with
	studied at	stenosis	occluded	patency rate	quantitative
	1 yr	N (%)			patency
Rosales 2009 ⁹	34	(3%)		(72%)	24.5
Neglén 2007⁵	135	(3%)	(17%)	(80%)	108
Kölbel, 2009 ¹⁰	40			(78%)	31.2
Wahlgren 2010 ¹¹	11	No chg		(61%)	6.7
Kurklinsky	91	(3%)	(19%)	(78%)	71
2011 ¹²					
Total	311			(77.9%)	242.1

 Table 15.5.2.c.
 Table 15.5.2.b
 Revised to Include In-stent Restenosis of 3%

15.5.3 Enrollment in the VIRTUS Study

Historically, about 50% of patient reported in mixed series are patients without thrombotic history⁵. The mix of thrombotic and non-thrombotic obstruction in those with chronic venous insufficiency is not known (varies from zero to approximately 50%). At the present time,

STE-HUM-007P US Clinical Protocol Revision C

Confidential

Page 42 of 70

we expect that approximately 74% (n=148 of our enrolled subjects will have a history of thrombo-embolic disease (i.e., be PT patients), and 26% (n=52) will not (i.e., be NT patients).

Though the specified hypothesis test and corresponding sample size calculation utilizes different performance goals for the PT and NT populations, Table 15.5.3 shows the combined patency rate in a control group adjusted to 74% PT and 26% NT patients. The overall or pooled patency rate is approximately 85%.

Author, Date	Weight	Limbs studied	Quantitative	
		at 1 yr	patency rate	
Non-thrombotic	.25	275	95.5%	
Thrombotic	.75	311	77.9%	
Total using Weights	1.00	302	(85.3%)	

Table 15.5.3. Combined Estimates of Tables 15.5.2.a and 15.5.2.c.

15.6 Hypotheses and Sample Size Estimate

The minimum required sample size is calculated based on the hypothesis-driven primary efficacy objective.

15.7 Primary Efficacy Endpoint

The minimum required sample size was determined using a Monte Carlo power simulation, conducted in R, testing the following hypothesis:

$$\begin{aligned} &\mathsf{H}_{\mathsf{0}}: q_{NT} * (p_{NT} - PG_{NT}) + q_{PT} * (p_{PT} - PG_{PT}) \leq 0 \\ &\mathsf{H}_{\mathsf{A}}: q_{NT} * (p_{NT} - PG_{NT}) + q_{PT} * (p_{PT} - PG_{PT}) > 0, \end{aligned}$$

where p_{NT} and p_{PT} are the observed 12-month patency rates for NT and PT subjects, respectively; PG_{NT} and PG_{PT} are pre-specified fixed performance goals for NT and PT subjects, respectively; and q_{NT} and q_{PT} , both are fixed weights for NT subjects (0.26) and PT subjects (0.74), respectively. The sample weights will not be adjusted based on actual enrollment rates.

The literature-based patency rate for the PT population is assumed to be 0.779, with corresponding performance goal (PG_{PT}) of 0.779 – 0.10 = 0.679. The literature-based patency rate for the NT population is assumed to be 0.955, with corresponding performance goal (PG_{NT}) of 0.955 – 0.10 = 0.855. Sample size is calculated to achieve at least 85% power at the one-sided 2.5% significance level:

STE-HUM-007P US Clinical Protocol Revision C

Characteristic	Value
Performance Goal	$PG_{PT} = 0.679; PG_{NT} = 0.855$
Confidence level α	0.025, one-sided
Power 1-β	≥85%
Estimated Vici patency rates	p_{PT} T = 0.779; p_{NT} = 0.955
RESULT: Sample Size	156 evaluable subjects

The estimated power is 84% for the primary efficacy endpoint (Patients who have a non-patent lesion prior to 12 months can be included in the analysis whether or not they are still being followed at 12 months because the 12-month patency status of their lesion is known).

In addition to rejecting the above hypothesis, overall success of the trial will also be determined based on whether a) the observed patency rate in the PT group is greater than 0.679, AND b) the *observed* patency rate in the NT group is greater than 0.855.

15.7.1 Primary Safety Endpoint

None of the case series in the literature used pre-specified adverse event definitions. The complication rate appears to be low, but there are no controlled studies to indicate what a true adverse event rate might be under controlled reporting conditions. It is expected that the true rate of the pre-specified safety endpoint will be approximately 1%. The primary safety evaluation will test the following hypothesis:

 $H_{O}:\ P_{Vici} \leq 0.94$

$$H_A: P_{Vici} > 0.94,$$

where P_{Vici} is the freedom from event rate of pre-specified safety events associated with use of the Veniti Vici Venous Stent and 0.94 is the prespecified performance goal. The hypothesis will be tested under a onesided, one-sample exact binomial test. The hypothesis will be tested at the 2.5% significance level, and approximately 170 subjects provide greater than 90% power. Power was calculated using PASS 2008 software.

15.7.2 Primary Secondary Endpoint

The primary secondary endpoint is the binary response variable based on achieving at least 50% improvement in VCSS. In a review of manuscripts by Hartung¹⁴, Rosales⁹, and Wahlgren¹¹, information on VCSS improvements are provided, as follows:

Hartung¹⁴: Median VCSS from 8.5 to 2 (n=44) Rosales⁹: Median VCSS from 9 to 1 (n=27) in group 1; median VCSS from 21 to 7 (n=7) Wahlgren¹¹: Mean VCSS from 9.1 to 6 (n=15)

However, distributional information (variance, specifically) is not provided. There also exists no generally agreed upon or accepted definition of a clinically meaningful improvement in VCSS to establish a performance goal. Therefore, Veniti will test a hypothesis test based on 50% of subjects improving by at least 50% as a means to demonstrate clinical benefit with the Veniti Vici Venous Stent. The formal hypothesis test takes the form:

$$H_0: P_{Vici} \leq 0.50$$

 $H_A: P_{Vici} > 0.50,$

where P_{Vici} is the proportion of subjects achieving at least 50% VCSS improvement (success rate), and 0.50 is the pre-specified performance goal. Based on the literature cited above, it is reasonable to assume a 62% success rate. Assuming this underlying rate of success, at least 156 evaluable subjects provides greater than 80% power to evaluate this objective at the 2.5% significance level under a one-sided, one-sample exact binomial test. Power was calculated using PASS 2008 software.

15.8 Evaluation of Endpoints

15.8.1 Primary Efficacy Endpoint

The primary efficacy endpoint for this study will be the primary patency rate at 12 months post-intervention. Stented limbs will be assigned the status of *patency failure* if they are known to have a patency failure event:

- Thrombosis including the stented area of the vein
- Re-intervention including the stented area
- Venous imaging study at any time through 12 months showing a restenosis of greater than 50%.

Patients will be assigned the status of *patency success* if their venous imaging study at 12 months showed no greater than 50% restenosis (and no prior study showed greater than 50% restenosis).

STE-HUM-007P US Clinical Protocol Revision C

In the per-protocol (PP) analysis, only patients that meet either of these two criteria will be included. Patients with no imaging study at 12 months and no patency failure event will be ignored in the analysis.

In the worst-case and tipping point analyses, all patients will be included. Patients who were ignored in the PP analysis will be treated as patency failures.

Both the PP and worst-case analyses will test the following hypotheses:

$$\begin{aligned} \mathsf{H}_{0} &: q_{NT} * (p_{NT} - PG_{NT}) + q_{PT} * (p_{PT} - PG_{PT}) \le 0 \\ \mathsf{H}_{A} &: q_{NT} * (p_{NT} - PG_{NT}) + q_{PT} * (p_{PT} - PG_{PT}) > 0, \end{aligned}$$

where p_{NT} and p_{PT} are the observed 12-month patency rates for NT and PT subjects, respectively; PG_{NT} and PG_{PT} are pre-specified fixed performance goals for NT and PT subjects, respectively; and q_{NT} and q_{PT} , both are fixed weights for NT subjects (0.26) and PT subjects (0.74), respectively. The sample weights will not be adjusted based on actual enrollment rates.

The hypothesis test for this endpoint will be tested using a one-sided weighted Z-test at the 0.025 significance level. The test statistic for this hypothesis test is:

$$Z = \frac{q_{NT} * (p_{NT} - PG_{NT}) + q_{PT} * (p_{PT} - PG_{PT})}{\sqrt{q_{NT}^2 * \frac{PG_{NT}(1 - PG_{NT})}{n_{NT}} + q_{PT}^2 * \frac{PG_{PT}(1 - PG_{PT})}{n_{PT}}}$$

where p_{NT} is the proportion of successes in the NT population, PG_{NT} is the performance goal of 85.5% for the NT population, q_{NT} is the predefined weight of 0.266 for the NT population, p_{PT} is the proportion of successes in the PT population, PG_{PT} is the performance goal of 67.9% for the PT population, q_{PT} is the pre-defined weight of 0.74 for the PT population.

The p-value for the one-sided hypothesis test will be calculated as $\Phi(-Z)$, where Φ is the normal cumulative distribution function.

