Reference Vein Diameter (RVD)	Reference Vein Diameter (RVD) is defined as the normal diameter of the target vessel (CIV, EIV, or CFV)
Procedural technical success	Achievement of a final residual target vessel diameter stenosis of ≤50% as measured on the post procedural venogram, without skipped lesion regions, with placement of the study device alone with or without post-stenting balloon dilation as needed
POST-PROCEDURAL DEFINITION	DNS
Term	Definition
Device or procedure related death	Death specifically attributable to the Veniti Vici Venous Stent System or the stent placement procedure
Late technical success	 Absence of device movement >10mm related to anatomical landmarks or any migration leading to symptoms or requiring therapy
	 Absence of stent occlusion by thrombosis or restenosis, defined as reduction in treated segment lumen more than 50% from the post-procedure vessel lumen diameter as measured by post-procedural venogram or DUS
	 Structural integrity, defined as the absence of pinching (focal compression), recoil (poor radial resistive force) or kinking (stent bending upon itself) that results in >50% diameter reduction of the stent, or fracture
Patency (Primary Endpoint)	At 12 months post-intervention, freedom from occlusion by thrombosis AND freedom from surgical or endovascular intervention on target vessel with re-stenosis or stent occlusion to maintain patency AND freedom from in stent diameter stenosis more than 50% as measured by venogram. For patients refusing the venographic assessment at 12 months, DUS-determined patency will be used instead

Rate of intervention lesion (RIL)	Re-intervention within the target vessel with in-stent stenosis or thrombosis to achieve patency (constitutes failure on the primary endpoint)
Rate of intervention of extremity (RIE)	Re-intervention of a non-target lesion venous segment of the ipsilateral (target) extremity required to maintain ipsilateral extremity venous outflow (does NOT constitute failure of the primary endpoint)
In-stent stenosis (primary endpoint)	Non-occlusive reduction in the treated segment lumen diameter more than 50% from the post-procedural vessel lumen diameter per venogram or DUS
In-stent thrombosis (primary endpoint)	Occlusion of the stented target vessel due to thrombosis; early thrombosis is that which occurs ≤30 days; late thrombosis is that which occurs >30 days

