7 STUDY OBJECTIVE AND DESIGN

The VIRTUS trial is a prospective, multicenter, single arm, non-randomized study to define safety and efficacy of the Veniti Vici Venous Stent System in relation to predefined Objective Performance goals. The objective of this study is to assess the safety and efficacy of the Veniti Vici Venous Stent System in achieving patency of the target venous lesion in patients who present with clinically significant chronic non-malignant occlusion of the iliofemoral venous outflow tract.

7.1 **Primary Endpoint – Efficacy:**

The primary efficacy endpoint for this study will be the primary patency rate at 12 months post-intervention, defined as freedom from occlusion by thrombosis AND freedom from surgical or endovascular intervention on target vessel which are found to have re-stenosis or stent occlusion to maintain patency AND freedom from in-stent stenosis more than 50% by venogram. For patients refusing the venographic assessment at 12 months, DUS-determined patency will be used instead.

7.2 Primary Endpoint – Safety:

The primary safety endpoint for this study will be a composite endpoint of any Major Adverse Event within 30 days, as adjudicated by a Clinical Events Committee. Major Adverse Events are listed in Section 11.1.4.

7.3 Secondary Endpoint – Efficacy:

The formal secondary endpoint of this study is a binary response variable based on whether or not a subject achieves at least 50% improvement on the Venous Clinical Severity Scoring (VCSS) scale at 12 months post-intervention.

7.4 Ancillary Outcomes:

Procedural Endpoints

- Procedural technical success, defined as achievement of a final residual target vessel diameter stenosis of ≤50% as measured on the postprocedural venogram, without skipped lesion regions, with placement of the study device alone with or without post-stenting balloon dilation as needed
- 2. Lesion success defined as achievement of ≤50% residual diameter stenosis using any percutaneous method (including the use of non-study devices)
- 3. Procedural success defined as procedural technical success without the occurrence of major adverse event between the index procedure and discharge
- 4. Late technical success (through 12 months) defined as:
 - a. Absence of migration
 - b. Absence of stent embolization
 - c. Achievement of primary patency
 - d. Structural integrity, defined as the absence of:
 - i. Pinching, defined as focal compression of the stent with > 50% diameter reduction of the stent

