9.10 Interval Evaluation

At any point following the venous stenting procedure, the patient may present with symptoms of clinically significant obstruction of the target vessel. Patients with possible obstruction should undergo all medical examinations and interventions as deemed appropriate for medical care. All technical examinations (DUS, IVUS, or venograms) obtained during the course of the evaluation will be submitted as part of the case report form and will be submitted to the Core Laboratory for determination of primary endpoint.

Patients who undergo re-intervention, but who are found on Core Laboratory assessment to have vessel patency prior to the re-intervention will not be counted as a primary efficacy endpoint failure. Patients who undergo an interval evaluation but do not receive an intervention will have their status (patency/non-patency) determined by the Core Laboratory. Patients who are found to be patent by Core Laboratory analysis will continue in the study through 12 months.

Patients who undergo another intervention at any time prior to the 12 month evaluation, or who are found to have in-stent stenosis > 50%, by Core Laboratory assessment, will be considered to have failed the primary efficacy endpoint and will not be required to have further assessment of vessel patency or other secondary endpoints.

All patients will complete the 30-day safety assessment regardless of primary patency status.

9.11 24 Month Evaluation (730 days ± 90 days)

- Telephone follow-up for SAE assessment. May be performed in-person, at the discretion of the investigator.
- Duplex ultrasound to assess vessel patency. (Office or laboratory visit)

9.12 36 Month Evaluation (1,095 days ± 90 days)

- Telephone follow-up for SAE assessment. May be performed in-person, at the discretion of the investigator.
- Duplex ultrasound to assess vessel patency. (Office or laboratory visit)

STE-HUM-007P US Clinical Protocol Revision C

Confidential

Page 31 of 70

9.13 48 Month Evaluation (1,460 days ± 90 days)

• Telephone follow-up for SAE assessment. May be performed in-person, at the discretion of the investigator.

9.14 60 Month Evaluation (1,825 days ± 90 days)

• Telephone follow-up for SAE assessment. May be performed in-person, at the discretion of the investigator.

STE-HUM-007P US Clinical Protocol Revision C

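### The trial counts restenosis of exactly 50% as patent, while the performance goals are defined with 50% or more as failure: a small one-way mismatch in favour of the device

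*Combined protocol and SAP*

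**What the plan says.** **Trial endpoint.** Section 15.8.1 lists as a patency failure "Venous imaging study at any time through 12 months showing a restenosis of greater than 50" per cent, and defines success as "no greater than 50% restenosis (and no prior study showed greater than 50% restenosis". A reading of exactly 50% is therefore a success. Section 7.1 and the Section 2 synopsis use the same cut ("freedom from in-stent stenosis more than 50% by venogram"). So does Section 1, which defines in-stent stenosis as "Non-occlusive reduction in the treated segment lumen diameter more than 50% from the post-procedural vessel lumen diameter per venogram or DUS". Section 9.10 applies it to interval evaluations: patients "who are found to have in-stent stenosis > 50%, by Core Laboratory assessment" have failed.

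**Performance goals.** Section 15.5.2 builds the historical rates from patients "free from ≥50% stenosis (per venogram or DUS lumen diameter"). The stenosis columns of its tables carry the ≥50% sign, and the PT rate is lowered because "approximately 3% of asymptomatic patients had re-stenoses of 50% or greater". Section 15.7 subtracts 0.10 from the resulting 0.955 (NT) and 0.779 (PT) to give goals of 0.855 and 0.679.

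The cut is not mentioned in Section 15.6 or 15.7, and no adjustment is made for it. Section 16 gives no measurement precision or rounding rule for the core laboratories.

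**The concern.** This is a single-arm study, so the performance goals are its only comparator, and the comparison is fair only if both sides count the same events as failures. Here one reading gets two labels. At exactly 50% a limb is a failure in the definition behind the goal and a success in the trial. The reclassification goes one way: it can raise the observed patency rate and cannot lower it. If it happened often enough, a stent whose patency only equalled the goals would be declared successful more often than the nominal one-sided 2.5%.

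**Working it through.** **Inputs.** Goals 0.855 and 0.679, assumed true rates 0.955 and 0.779, weights 0.26 and 0.74, one-sided 0.025, and 156 evaluable subjects (Sections 15.7 and 15.8.1). The plan does not split the 156 by stratum. I assume 41 NT and 115 PT, from the weights.

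**1. The plan's power.** The statistic is Z = [0.26(p_NT − 0.855) + 0.74(p_PT − 0.679)] / s0, where

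s0 = √(0.26² × 0.855 × 0.145/41 + 0.74² × 0.679 × 0.321/115) = √(0.000204 + 0.001038) = 0.0352.

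The weighted excess needed is 1.96 × 0.0352 = 0.069, or 6.9 points. The normal approximation then gives power 0.850. Exact enumeration of the two binomials gives 0.870 at 41/115, 0.852 at 39/117 and 0.832 at 42/114. The plan states 84% in the text and at least 85% in the table, so its figure is reproduced.

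**2. A ceiling for the affected share.** The documents do not say how many readings fall at exactly 50%. Their tables do show how much stenosis of 50% or more the historical series recorded:

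- NT: (1 + 1% of 132)/275 = 2.32/275 = 0.84%.
- PT: 3% of (34 + 135 + 91), over 311 = 7.8/311 = 2.5%. These are the three series given a 3% share in the revised PT table.

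If the trial resembles these series, readings of exactly 50% cannot exceed these shares.

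**3. Weight of one patient.** Moving one PT patient from failure to success changes the PT rate by 1/115 = 0.87 points, and the weighted difference by 0.74 × 0.87 = 0.64 points, against the 6.9 needed. Even at the ceiling, the expected number moved is about 0.025 × 115 = 2.9 PT and 0.0084 × 41 = 0.3 NT patients.

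**4. False-success probability.** Suppose true patency, counted with 50% or more as failure, equals the goals. The trial's rule adds the share at exactly 50% to each stratum's success probability. The full rule requires Z > 1.96 and both observed rates above their goals (Section 15.7). Exact enumeration at 41/115 gives:

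| Fraction of the historical ≥50% share at exactly 50% | Added NT / PT (points) | False success, full rule |
|---|---|---|
| none | 0 / 0 | 2.2% |
| one tenth | 0.08 / 0.25 | 2.5% |
| one fifth | 0.17 / 0.50 | 2.8% |
| all (extreme) | 0.8 / 2.5 | 7.1% |

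The fractions are assumptions. The last row uses the shares rounded as shown; unrounded shares give 7.2%.

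**The case against.** The strongest reply is that this is a difference at one boundary value. Venograms, and duplex scans through 36 months, go to core laboratories. No section says that readings are rounded or graded in categories, and a continuous measurement will seldom equal 50%. That stands, and it is why the likely effect is small. It does not remove the mismatch, because no rule excludes such readings either.

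Second, the historical cut is itself uncertain. One sentence in Section 15.5.2 describes the same PT adjustment with stenosis above 50%. Two PT series are marked as not evaluated for stenosis, one of them studied patients only if symptomatic, and a footnote merely infers that two others assessed stenosis. This also stands: the source series may not all have used ≥50%. But the stated definition and the table headings do use it, and the goals rest on them.

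A reader might infer more than the documents support:

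- **An effect of 1 to 2 points in both strata.** This would give false-success rates of 4.1% and 7.4%. Even 1 point in NT exceeds the whole historical NT share of 0.84%. Two points is more than twice that share, and would also need about 80% of the PT share (2.0/2.5) at exactly 50%.
- **A clash with the entry criterion of ≥50%.** Entry stenosis is measured against the normal vein immediately peripheral to the lesion (Sections 1 and 9.4). In-stent stenosis is measured against the post-procedural lumen (Sections 1 and 9.5.3). They are different quantities.
- **That the trial fails a limb on stenosis alone.** Thrombosis and re-intervention are failures too, and the mismatch does not touch them.

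**Conclusion.** The point holds for the stenosis component of the primary endpoint. As written, exactly 50% is a failure in the definition behind the goals and a success in the trial, and the difference can only favour the device. The likely size is a few tenths of a point of false-success probability: 2.2% to about 2.5–2.8% if one tenth to one fifth of the historical share lies at exactly 50%, and near zero with unrounded readings. About 7.1% is the extreme within the historical shares and should not be read as an expectation.

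These figures rest on the assumed 41/115 split, on the trial having stenosis shares like those in the historical tables, and on those tables having used ≥50% as stated. The documents do not settle the last two. The point is worth correcting because the remedy is nearly free, and it gives no reason to change the sample size.

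**What to change.** In Section 1 (patency and in-stent stenosis), the Section 2 synopsis, and Sections 7.1, 9.10 and 15.8.1, make the stenosis failure cut 50% or more, and the success rule in 15.8.1 less than 50%, so that both equal the cut in Section 15.5.2. Correct the one sentence in 15.5.2 that uses the stricter wording. State that unrounded core-laboratory values are scored. Leave the entry criterion alone, since it uses a different reference diameter, and say whether the other 50% cuts (residual stenosis, structural integrity) stay as they are.

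If the primary definition is kept, the minimum is to state how exactly 50% is classed and to pre-specify a sensitivity analysis of the full efficacy rule counting 50% or more as failure.

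The cost is wording in five sections, with no new visits, imaging or subjects. Observed patency may be slightly lower. The power calculation need not change, because its assumed rates of 0.955 and 0.779 are the literature rates already defined on the ≥50% cut. Raising the goals instead is not practical, because it needs the unknown share at exactly 50%.
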